### **Repetition of Imputations (K)**

Repetition of imputations, K, must be determined in advance. When estimating the overall variance of multiple imputation, the additional sampling variance is the between-imputation variance divided by K. This value represents the sampling error associated with the overall or average coefficient estimates. It is used as a correction factor for using a specific number of imputations. The more imputations (K) are conducted, the more precise the parameter estimates will be. For example, with a 1% power falloff tolerance in multiple imputation, as compared to an infinite number of imputations, multiple imputation requires 20 repetitions of imputation for 30% missing information and 40 repetitions for 50% missing information. In the usual clinical settings expecting less than 30% missing information, K = 30 repetitions are deemed sufficient.

When missingness exceeds 30%, depending on the power falloff tolerance level, number of repetitions may need to be increased. Recent research suggested that the number of repetitions (K) should be at least equal to the percentage of missing.

## **2.4 Derivation of Response Status and Non-Responder Imputation**

For each 'complete' dataset, the imputed post-baseline values will be rounded to the same precision as the observed data. Response status (e.g., EASI 90 at each visit) will be determined accordingly.

The imputed response status for missing due to reasons other than COVID-19 or any other missing data that can be reasonably assumed to be Missing at Random will be overridden by non-responder imputation (Section 9.2) to ensure that multiple imputation is only applied to missing due to COVID-19 or any other missing data that can be reasonably assumed to be Missing at Random:

Using NRI approach, all missing due to reasons other than COVID-19 or any other missing data that can be reasonably assumed to be Missing at Random will be categorized as non-responders. In addition, subjects whose change/percent change from Baseline cannot be calculated because of a missing Baseline will be considered as a non-responder at all post-baseline visits unless the post-baseline value is zero.

The only exception is that a subject will be categorized as a responder for the visit if the subject is a responder both before and after an SAP-specified visit window in Period 1.

## **2.5 Analysis**

The statistical analysis will use the Cochran-Mantel-Haenszel (CMH) test adjusted by the stratification factors derived from actual values.

### 2.5.1 Analysis of Each Dataset

For each of the K 'complete' datasets, the CMH test will be used to estimate the treatment difference (Upadacitinib versus Dupilumab) and the corresponding standard error.

### 2.5.2 Synthesis of Results for Statistical Inference

The results from the K 'complete' datasets will be synthesized using the SAS procedure PROC MIANALYZE, following Rubin's formula, to derive the MI estimator of the treatment difference for the final inferences.

#### **Rubin's formula**

We fit the analysis model to the kth 'complete' dataset, denoting the estimate of the treatment difference q by  $\tilde{\theta}_k$  from the kth 'complete' dataset, and denoting the corresponding estimate of the variance as  $V_k$ .

The MI estimator of q (point estimator obtained from PROC MIANALYZE),  $\tilde{\theta}_{MI}$ , is the average of the K individual estimators:

$$\tilde{\theta}_{MI} = \frac{1}{K} \sum_{k=1}^K \tilde{\theta}_k.$$

The estimated variance of  $\tilde{\theta}_{MI}$ , is a combination of the between- and within-imputation variability as follows:

$$V_{MI} = W + \left(1 + \frac{1}{K}\right)B,$$

where  $W = \frac{1}{K} \sum_{k=1}^K V_k$  is the within-imputation variability and

$B = \frac{1}{K-1} \sum_{k=1}^K (\tilde{\theta}_k - \tilde{\theta}_{MI})^2$  is the between-imputation variance.

It has been shown that the statistic

$$T = \frac{\tilde{\theta}_{MI} - \theta}{\sqrt{V_{MI}}}$$

has an approximate  $t_v$  distribution where  $v = (K - 1)(1 + \frac{W}{B})^2$ . Statistical inference, including hypothesis testing and confidence intervals for the treatment effect, will be based on this T-statistic.

### 3.0 Sample SAS Code

```

/*****/
/*IMPUTATION ALGORITHM*/
/*****/
/*NOTE: THIS APPROACH REQUIRES NO MISSING IN CATEGORICAL COVARIATES AND
REQUIRES AT LEAST ONE OBSERVATION IN BASELIBE OR ONE OF THE POST
BASELINE VISIT*/

/*PRE AUGMENTATION CREATE DUMMY FOR CATEGORICAL VARIABLES*/
/*****/
DATA EASI_2; SET EASI;
  /*THE MCMC STATEMENT BELOW ASSUMES MULTI VARIATE NORMAL*/
  /*IF TREATMENT OR ANY COVARIATES ARE CATEGORICAL WITH L>2 LEVELS*/
  /*NEED TO CREATE L 1 DUMMY VARIABLES*/
  /*HERE, TREATMENT (TRT01PN) HAS 2 LEVELS, SO WE NEED 1 DUMMY
VARIABLES*/
  IF TRT01PN=1 THEN TRT1=1;
  ELSE TRT1=0;
RUN;

/*AUGMENTATION STEP TO HAVE 30 MONOTONE MISSING DATASETS*/
PROC MI DATA=EASI_2 OUT=EASI_MONO NIMPUTE=30 SEED= 1001 /*RANDOM SEED
PRE DEFINED*/
  ROUND=. . . 0.1 0.1 0.1 0.1 0.1 0.1 /*VALUE ROUND TO 1ST DECIMAL*/
  MIN=. . . 0 0 0 0 0 0 /*MINIMUM VALUE OF EASI IS 0*/
  MAX=. . . 72 72 72 72 72 72; /*MAXIMUM VALUE OF EASI IS 72*/
  MCMC IMPUTE=MONOTONE ;
/*NOTE: CATEGORICAL VARIABLES SUCH AS TRT1 ARE DUMMY, CREATED ABOVE*/
/*NOTE: ALL OTHER NON DUMMIED COVARIATES MUST BE CONTINUOUS*/
/*SUPPOSE STRATAN (NUMERIC VARIABLE FOR STRATA) HAS ONLY 2 LEVELS, NO
NEED TO CREATE DUMMY*/
  VAR TRT1 AGEGR1N VIGAGR1N BASE WK2 WK4 WK8 WK12 WK16;
/*CAUTION TO USE THE "BY" STATEMENT IN MCMC: */
/*MVN MODEL IS FITTED WITHIN EACH 'BY' GROUP, INSTEAD OF ACROSS ALL
GROUPS*/
RUN;

```

```

/*IMPUTATION STEP  DETERMINE IMPUTATION DISTRIBUTION AND RANDOMLY
IMPUTE MISSING VALUE TO GENERATE 'COMPLETE' DATASETS*/
/*****/
PROC MI DATA=EASI_MONO OUT=EASI_FULL NIMPUTE=1 SEED= 9001 /*RANDOM SEED
PRE DEFINED*/
  ROUND=. . . 0.1 0.1 0.1 0.1 0.1 0.1 /*VALUE ROUND TO 1ST DECIMAL*/
  MIN=. . . 0 0 0 0 0 0 /*MINIMUM VALUE OF EASI IS 0*/
  MAX=. . . 72 72 72 72 72 72; /*MAXIMUM VALUE OF EASI IS 72*/
  MINMAXITER=1000;
  CLASS TRT01PN AGEGR1N VIGAGR1N;
  VAR TRT01PN AGEGR1N VIGAGR1N BASE WK2 WK4 WK8 WK12 WK16;
  MONOTONE REG (WK2 WK4 WK8 WK12 WK16); /* IMPUTED SEQUENTIALLY, FROM
WK 2 TO 16, WITH COVARIATES CONSTRUCTED FROM THE CORRESPONDING PRECEDING
VARIABLES*/
  BY IMPUTATION ; /*FOR EACH OF THE 30 MONOTONE
MISSING DATASETS, IMPUTE A 'COMPLETE' DATASET*/
RUN;

/*DETERMINE DICHOTOMOUS RESPONSE STATUS, EASI 90*/
DATA ALL; SET EASI_FULL;
  IF 0<=WK2<=0.9*BASE THEN EASI90_2=1;
  ELSE EASI90_2=0;
  IF 0<=WK4<=0.9*BASE THEN EASI90_4=1;
  ELSE EASI90_4=0;
  IF 0<=WK8<=0.9*BASE THEN EASI90_8=1;
  ELSE EASI90_8=0;
  IF 0<=WK12<=0.9*BASE THEN EASI90_12=1;
  ELSE EASI90_12=0;
  IF 0<=WK16<=0.9*BASE THEN EASI90_16=1;
  ELSE EASI90_16=0;
RUN;

/*****
*/
/* DATA HANDLING STEPS TO MERGE COVID 19 or Other MAR STATUS OMITTED
*/
/* PLACE TO ADD DATA HANDLING AND MERGING STEPS
*/
/*****
*/

/*FOR MI, SKIP THE FOLLOWING CODE, PROCEED TO THE CODE AFTER ANALYSIS
MODEL *//*OVERRIDE MISSING VALUES NOT DUE TO COVID 19 or Other MAR WITH
TRADITIONAL NRI*/
DATA ALLF; SET ALL;
  /*COVID19_XX='Y' IF MISSING AT WEEK XX IS DUE TO COVID 19 or Other
MAR; IF NOT, OVERRIDE WITH TRADITIONAL NRI*/

```

```

    IF COVID19_2 NE 'Y' THEN EASI90_2=EASI90NRI_2;
    IF COVID19_4 NE 'Y' THEN EASI90_4=EASI90NRI_4;
    IF COVID19_8 NE 'Y' THEN EASI90_8=EASI90NRI_8;
    /*VARIABLE EASI90NRI XX: TRADITIONAL NRI DATA AT WEEK XX, WHICH COVERS
    THE SPECIAL HANDLING SUCH AS THE BEFORE AND AFTER EXCEPTION*/
    IF COVID19_12 NE 'Y' THEN EASI90_12=EASI90NRI_12;
    IF COVID19_16 NE 'Y' THEN EASI90_16=EASI90NRI_16;
  RUN;
  PROC SORT DATA=ALLF; BY _IMPUTATION_ SUBJID; RUN;

  /*****/
  /*ANALYSIS MODEL*/
  /*****/

  /*KEY CODE: ANALYZING EACH 'COMPLETE' DATASET*/
  /*****/
  /*COMPARE TREATMENT GROUPS 1 (Dupilumab) AND 2 (Upadacitinib) ONLY*/
  DATA ALL; SET ALL;
    WHERE TRT01PN IN (1,2);
  RUN;

  /*INDIVIDUAL LEVEL DATA > # OF RESPONDERS & # OF SUBJECTS, TO BE READ
  IN TO PROC STDRATE*/
  PROC FREQ DATA=ALL;
    BY IMPUTATION ;
    TABLES TRT01PN*AGEGR1N*VIGAGR1N*EASI90_16/LIST NOCUM NOPRINT
  OUT=COUNT_TABLE;
    /*WEEK 16 RESULTS AS AN EXAMPLE*/
  RUN;
  DATA COUNT_TABLE; SET COUNT_TABLE;
    DROP PERCENT;
  RUN;
  PROC TRANSPOSE DATA=COUNT_TABLE OUT=FREQ_TABLE PREFIX=RESP;
  ID EASI90_16;
  BY IMPUTATION_ TRT01PN AGEGR1N VIGAGR1N;
  VAR COUNT;
  RUN;
  DATA FREQ_TABLE1; SET FREQ_TABLE;
    CASE=RESP1;
    SIZE=SUM(RESP0, RESP1);
    KEEP _IMPUTATION_ TRT01PN AGEGR1N VIGAGR1N CASE SIZE;
  RUN;

  /*RE ORDER TO SET 1 (Dupilumab) AS THE REFERENCE GROUP*/
  DATA FREQ_TABLE2; SET FREQ_TABLE1;
    IF TRT01PN=2 THEN TRT01PN=0;
  RUN;

  /*CALCULATE THE COMMON RISK DIFF FOR EACH COMPLETE DATASET*/

```

```
PROC STDRATE DATA=FREQ TABLE2  
  METHOD=MH STAT=RISK EFFECT=DIFF;  
  BY _IMPUTATION_;  
  POPULATION GROUP=TRT01PN EVENT=CASE TOTAL=SIZE;  
  STRATA AGEGR1N VIGAGR1N / ORDER=DATA STATS (CL=NONE) EFFECT;  
  ODS OUTPUT EFFECT=EFFECT;  
RUN;
```

```
/*COMBINING RESULTS USING PROC MIANALYZE*/  
/*****  
PROC MIANALYZE DATA=EFFECT;  
  ODS OUTPUT PARAMETERESTIMATES=RISK_DIFF_MH;  
  MODELEFFECTS RISKDIFF;  
  STDERR STDERR;  
RUN;
```

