## **2.0 Study Objectives and Design**

### **2.1 Study Objectives, Hypotheses and Estimands**

The primary study objective, related to Study Period 1, is to assess the efficacy and safety of upadacitinib, initiated at 15 mg once daily (QD) and dose adjusted based on clinical response, compared with dupilumab as per its label. An additional objective, related to Study Period 2, is to assess the efficacy and safety of upadacitinib, initiated at 15 mg QD and dose adjusted based on clinical response, in subjects with inadequate response to dupilumab and treated at 30 mg QD in subjects with inadequate response to upadacitinib in Period 1. The primary efficacy objective is based on the achievement of an at least 90% reduction in EASI from baseline (EASI 90) and a Worst Pruritus Numerical Rating Scale of 0 or 1 (WP-NRS 0/1) at Week 16 with the treatment of upadacitinib compared with dupilumab in the Intent-to-Treat (ITT) Population, which consists of all randomized

subjects. The secondary efficacy objectives are based on ranked secondary endpoints as defined in Section 3.2 (below) with the treatment of upadacitinib compared with dupilumab in the ITT Population.

The hypothesis corresponding to the primary efficacy endpoint (Section 3.1) is:

The proportion of subjects achieving EASI 90 and WP-NRS 0/1 at Week 16 in those treated with upadacitinib is greater than those treated with dupilumab.

The estimand corresponding to the primary endpoint is defined using the composite variable strategy, as follows:

Difference in the proportion of subjects achieving EASI 90 and WP-NRS 0/1 at Week 16 without the use of rescue medication between upadacitinib and dupilumab in the adolescents and adult subjects with moderate to severe AD who have inadequate response to systemic therapy.

The hypotheses and estimands corresponding to the ranked secondary endpoints are summarized below.

Hypotheses: the proportion of subjects achieving each ranked endpoint in those treated with upadacitinib is greater than those treated with dupilumab.

Estimands: Difference in proportion of subjects achieving each of ranked secondary endpoints without the use of rescue medication between upadacitinib and dupilumab in adolescents and adult subjects with moderate to severe AD who have inadequate response to systemic therapy.

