### **2.2 Multiple Imputation (MI) and MAR Assumption**

When a dichotomized variable is derived from a continuous scale, for example, EASI 90 (at least a 90% reduction in EASI relative to Baseline), the multiple imputation will be applied to the original scale, EASI (ranges from 0 - 72) assuming multivariate normal distribution. Then the dichotomized variable will be derived from the imputed value.

The MI procedure assumes that the data are missing at random (MAR). That is, for an outcome variable Y, the probability that an observation is missing depends only on the

observed values of other variables, not on the unobserved values of the outcome variable Y. Statistical inference from the MI procedure is valid under the MAR assumption.

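### The sample SAS code in SAP Appendix H codes EASI 90 as a 10% reduction, and its NRI-MI analysis step never reads the data set holding the non-responder override

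*SAP*

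**What the plan says.** **Definition.** SAP 2.1 bases the primary efficacy objective partly on "an at least 90% reduction in EASI from baseline (EASI 90". SAP Appendix H, section 2.2, gives the same meaning: "EASI 90 (at least a 90% reduction in EASI relative to Baseline". It adds that imputation is done on the original EASI scale of 0 to 72 and that response is then derived from the imputed score.

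**Missing data.** NRI-MI is the primary approach (SAP 9.3.2). Under SAP 9.2 and Appendix H, section 2.4, multiple imputation counts only where data are missing because of COVID-19 or can be taken as missing at random. Other missing values are reset to non-response, apart from the exception for subjects who respond both before and after the visit window.

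**Code.** Appendix H, section 3.0, derives response with "IF 0<=WK2<=0.9*BASE THEN EASI90_2=1" and the same form at Weeks 4, 8, 12 and 16, ending with "IF 0<=WK16<=0.9*BASE THEN EASI90_16=1". The override is then built in a new data set, "DATA ALLF; SET ALL", with lines such as "IF COVID19_16 NE 'Y' THEN EASI90_16=EASI90NRI_16". A comment addresses the MI sensitivity analysis: "FOR MI, SKIP THE FOLLOWING CODE, PROCEED TO THE CODE AFTER ANALYSIS". The responder counts come from "PROC FREQ DATA=ALL".

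**The concern.** The code contradicts the SAP in two places.

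1. The cut-off is on the wrong side of the scale. A score at or below 0.9 times Baseline is a 10% improvement, not a 90% improvement.
2. The override is created but not used. ALLF is sorted and never read again, while the analysis works from ALL.

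EASI 90 is one of the two components of the primary endpoint, and it is ranked secondary endpoint 1 (Week 16) and 6 (Week 4). This listing is the only printed derivation of it. It carries seeds 1001 and 9001, which SAP Appendix D assigns to the EASI 90 component of the primary endpoint under NRI-MI; the MI sensitivity analysis has 1015 and 9015. It also uses this trial's visits, arms and strata, so reuse by a programmer is realistic.

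**Working it through.** **The plan's design figure.** The SAP 2.4 power statement reproduces: 440 per arm, 12% versus 29%, two-sided 0.05 gives power above 0.999, consistent with the stated figure of more than 90%. Nothing below depends on it.

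**Inputs.** The EASI 90 definition (SAP 2.1; Appendix H, 2.2); the coded rule and the 0 to 72 bounds in PROC MI (Appendix H, 3.0); minimum Baseline EASI of 16 (Protocol 5.1, criterion 7); 440 per arm (SAP 2.3).

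**Step 1: the cut-off.** Score ≤ c × BASE is the same as reduction ≥ 1 − c. With c = 0.9 the reduction is at least 10%; a 90% reduction needs c = 0.1. The WK variables are raw scores bounded at 0 and 72, so 0.9 cannot be a percent-change threshold.

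| Baseline EASI | Defined cut-off (0.1 × BASE) | Coded cut-off (0.9 × BASE) |
|---|---|---|
| 16 | 1.6 | 14.4 |
| 30 | 3.0 | 27.0 |
| 72 | 7.2 | 64.8 |

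At Baseline 16 the correct EASI 75 and EASI 50 cut-offs are 0.25 × 16 = 4.0 and 0.5 × 16 = 8.0. A score of 12.0 is a reduction of 1 − 12/16 = 25%. It fails both, yet lies below 14.4 and is coded as EASI 90.

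**Step 2: the data flow.** EASI_FULL becomes ALL (response derived). ALL becomes ALLF (override applied, sorted, then nothing further). Separately, ALL is filtered to the two arms and goes to PROC FREQ, PROC STDRATE and PROC MIANALYZE. No analysis step reads ALLF.

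**Step 3: both corrections are needed.** Take Baseline 30 and Week 16.

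| Subject | 0.9, ALL | 0.9, ALLF | 0.1, ALL | 0.1, ALLF |
|---|---|---|---|---|
| Observed 15.0 (50% reduction) | responder | non-responder | non-responder | non-responder |
| Missing, not COVID-19/MAR, imputed 2.0 | responder | non-responder | **responder** | non-responder |
| Missing, flagged COVID-19/MAR, imputed 15.0 | responder | **responder** | non-responder | non-responder |

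Correcting only the cut-off leaves the second subject wrong. Correcting only the data set leaves the third wrong. The ALLF columns assume that EASI90NRI, whose derivation is not printed, is correct.

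**Step 4: reach by route.**

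- (a) As printed, reading ALL: the 10% rule classifies every subject, observed or imputed.
- (b) MI sensitivity analysis, which skips the override: the same as printed, subject to the separate rescue rule in SAP 9.2.
- (c) Reading ALLF: every value not flagged is replaced by EASI90NRI, so only flagged, imputed values are affected.

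**Step 5: ceiling for route (c).** Let f be the share of an arm that is imputed and p its true EASI 90 rate; both are assumptions. The coded rate can rise by at most min(f, 1 − p). For f = 1%, 5% and 10% this equals f for any p up to 90%: 440 × f = 4.4, 22 and 44 extra responders.

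At an assumed p = 40% the ceilings are 41%, 45% and 50%. Check at f = 10%: 176 true responders, all observed, plus 44 imputed non-responders coded as responders, is 220/440 = 50%. If imputed subjects share the arm's true rate and all are coded responders, p + f(1 − p) gives 40.6%, 43.0% and 46.0%.

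No rate is given for (a) or (b), because the documents give no EASI distribution.

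**The case against.** The strongest reply is that this is labelled sample code and the governing text is right throughout. The listing cannot run as it stands: the merging of COVID-19/MAR status is marked as omitted, and the override variables are never created. In the second PROC MI call a semicolon also cuts off an option. A programmer working from SAP 9.2 and Appendix H, section 2.4, would reach the correct rule. The printed seeds belong only to the composite's EASI 90 component (ranked secondaries 1 and 6 have 1003/9003 and 1008/9008), no WP-NRS or composite step is printed, and composite responders cannot exceed WP-NRS 0/1 responders. Reading ALL is right for the MI analysis, where SAP 9.2 also sets subjects to non-response after rescue. A gross error would clash with the planned NRI sensitivity analysis and with EASI 75.

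Much of this stands. No wrong trial result is shown, and in routes (a) and (b) the error should be conspicuous. But the cut-off and the data set name are printed, not omitted, and completing the merge changes neither. Different seeds do not alter the fact that this is the only EASI 90 derivation on paper. Two forms are less easily seen: the wrong cut-off confined to imputed values, and the unread override once the cut-off is corrected. The second would give the nominal primary analysis the MI analysis's treatment of missing data. Such missing data are foreseeable, since Protocol 5.6 takes subjects who stop study drug out of the study.

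**Conclusion.** The concern holds on both counts. The code's EASI 90 rule is a 10% reduction at all five visits, and the NRI-MI analysis as printed ignores its own override. The cut-offs (1.6 defined, 14.4 coded at Baseline 16) follow from the documents alone. The ceilings of 1, 5 and 10 points apply only to route (c) and rest on assumed imputed shares. The effect on the composite endpoint and on the difference between arms is not quantified, and the production program may be free of both faults. It is rated must-fix because the printed rule contradicts the endpoint definition and the primary missing-data rule, not because a wrong result has been found. Sample size and power are unaffected.

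**What to change.** In SAP Appendix H, section 3.0:

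1. Replace 0.9 by 0.1 in all five EASI 90 statements.
2. Make the NRI-MI analysis (the DATA step that selects the arms, and PROC FREQ) read ALLF. Keep ALL for the MI sensitivity analysis, with the post-rescue non-response rule of SAP 9.2 applied.
3. Before use, compare the program's observed-case EASI 90 rates, by arm and visit, with the directly derived endpoint.

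The cost is five constants, a data set name and one routine check. Endpoint, sample size and trial conduct stay as they are, and there is no downside.

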## **9.2 Handling of Missing Data**

In Period 1, missing values and visits after the rescue will be handled by non-responder imputation (NRI) except for missing values due to COVID-19 or any other missing data that can be reasonably assumed to be Missing at Random, which will be handled by multiple imputation (NRI-MI).

- The NRI-MI will categorize any subject who does not have an evaluation during a pre-specified visit window (either due to missing assessment or due to early withdrawal from the study) as a non-responder for the visit. The only exceptions are: 1) when the subject is a responder both before and after the visit window, the subject will be categorized as a responder for the visit. 2) missing data due to COVID-19 infection or logistical restriction or any other missing data that can be reasonably assumed to be Missing at Random, will be handled by Multiple Imputation. In addition, all assessments after the start of rescue medications will not be included in the analyses; as a result, subjects will be counted as non-responders thereafter and will not be imputed by MI. Random seeds are provided in [Appendix D](#). NRI-MI is the primary approach to handle missing data for categorical endpoints in Period 1.
- Non-responder Imputation (NRI): NRI will be performed in the same way as NRI-MI without the exception #2 above. That is, missing due to COVID-19 infection or logistical restriction or any other missing data that can be reasonably assumed to be Missing at Random, will also be counted as non-responders. The NRI is a missing data handling method in a sensitivity analysis for the primary endpoint.

Subjects whose change/percent change from Baseline cannot be calculated because of a missing Baseline will be considered as a non-responder at all post-baseline visits in both NRI-MI and NRI approaches.

Multiple Imputation (MI): another missing data handling method performed in a sensitivity analysis for the primary endpoint. Markov Chain Monte Carlo (MCMC) will be first applied to augment data into monotonic missing pattern and PROC MI will be used to generate 30 datasets using the regression method.

- The imputation is done in two steps for the primary endpoint.
- Step 1: The EASI 90 and WP-NRS 0/1 (based on weekly average) are imputed separately.

For example, for EASI 90, the variables to be included in the imputation model are treatment group, major stratum (vIGA-AD categories and age),

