Baseline, and measurements at each visit in Period 1. The random seed for MCMC and the random seed for PROC MI are specified in [Appendix D](#). The imputed post-baseline measurements will be rounded to the same precision as the observed data before the determination of responder status. WP-NRS 0/1 will be imputed by the same imputation model as EASI 90.

- Step 2: After obtained the EASI 90 and WP-NRS 0/1 (based on weekly average) at Week 16 based on MI imputed values separately, subjects will be characterized as responders or non-responders based on MI imputed datasets. Using the Cochran-Mantel-Haenszel (CMH) model adjusted by main stratification factors (vIGA-AD categories and age), the imputed endpoints will be analyzed using each of the 30 datasets. SAS PROC MIANALYZE will be used to generate the final inferences of the risk difference between upadacitinib and dupilumab. Note that measurements will be considered as missing after the first dose of rescue treatment before MI. Regardless of MI imputed values, subjects after receiving rescue medications will be counted as non-responders.

In Period 2, the primary approach to handle missing data is Observed Cases (OC).

- The OC analysis will not impute values for missing evaluations, and thus a subject who does not have an evaluation at a scheduled visit will not be included in the OC analysis for that visit. The OC analysis will be performed for all variables and will not include values after more than 1 day after discontinuation of study drug.

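### The sample SAS code for the primary NRI-MI analysis builds the non-responder override in one data set (ALLF) and then analyses another (ALL)

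*SAP*

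**What the plan says.** SAP 9.2 names NRI-MI as the primary approach for categorical endpoints in Period 1, which covers the primary endpoint and the eight ranked secondary endpoints. On rescue it says that "subjects will be counted as non-responders thereafter and will not be imputed by MI". For the MI sensitivity analysis it repeats the rule: "Regardless of MI imputed values, subjects after receiving rescue medications will be counted as non-responders".

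Appendix H 2.4 says that imputed status for other kinds of missingness "will be overridden by non-responder imputation (Section 9.2"), so that multiple imputation applies only to COVID-19 or missing-at-random data.

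Appendix H 3.0 gives the only code for this method, worked for EASI 90. The override step opens with "DATA ALLF; SET ALL", and its Week 16 line is "IF COVID19_16 NE 'Y' THEN EASI90_16=EASI90NRI_16". A comment says that the NRI variables also carry "THE SPECIAL HANDLING SUCH AS THE BEFORE AND AFTER EXCEPTION". Another comment sends only the MI sensitivity analysis round this block: "FOR MI, SKIP THE FOLLOWING CODE, PROCEED TO THE CODE AFTER ANALYSIS". The counts for the analysis then come from "PROC FREQ DATA=ALL".

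**The concern.** The text and the code specify two different analyses. If the code is reused with its data-set names, subjects whom the SAP calls non-responders keep imputed responses in the primary analysis. The reported difference and its confidence interval would then not follow the stated rule.

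The MI sensitivity analysis would also lose its purpose. With both paths run as printed, it differs from NRI-MI only by seeds: for EASI 90, 1001 and 9001 against 1015 and 9015 (Appendix D). It would add no independent check on the NRI part of the primary method. The NRI sensitivity analysis is not touched by the slip and remains a check.

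**Working it through.** **Data flow, in printed order**

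| Step | Reads | Writes | Content |
|---|---|---|---|
| Derive response | `EASI_FULL` | `ALL` | Imputed status for every missing value |
| Override | `ALL` | `ALLF` | NRI status wherever the COVID-19/MAR flag is not Y |
| Sort | `ALLF` | `ALLF` | Last use of `ALLF` |
| Select treatments | `ALL` | `ALL` | No override |
| Count, transpose, STDRATE, MIANALYZE | `ALL` | Result | No override |

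No printed statement switches the input to `ALLF` for NRI-MI. The placeholder for omitted data handling comes before the override step, so it cannot change what is read later.

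**Rescue.** No printed line sets response to 0 after rescue. In the NRI-MI path, the only possible carrier is the NRI variable, which is discarded. The MI path skips the block altogether. The placeholder could hold a rescue rule, but it names only COVID-19/MAR status. Reading `ALLF` may not be enough either, because the override fires only when the flag is not Y. On the flag's printed definition, a rescued subject who misses Week 16 for COVID-19 keeps an imputed response, unless the flag is derived to exclude rescued subjects, which is not shown.

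**Zero cells.** The count table is built without the SPARSE option. For a treatment-by-stratum cell with 6 subjects and no responders, `RESP0` = 6 and `RESP1` is missing. Then `SIZE` = SUM(6, missing) = 6, but `CASE`, a plain copy of `RESP1`, is missing and not 0. At the 12% planning rate, the chance that a dupilumab cell has no responders is 0.88^n. For assumed cell sizes of 10, 18 and 30 this is 0.279, 0.100 and 0.022.

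**The plan's own figure.** SAP 2.4 gives 440 per arm, 12% against 12 + 17 = 29%, and two-sided 0.05. With the pooled two-proportion formula:
- Standard error under the null = sqrt(2 × 0.205 × 0.795 / 440) = 0.0272.
- Standard error under the alternative = sqrt((0.12 × 0.88 + 0.29 × 0.71) / 440) = 0.0266.
- z = (0.17 − 1.96 × 0.0272) / 0.0266 = 4.38, so power is 99.999%. This agrees with the stated figure of more than 90%.

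**Possible shift (illustration).** Let p be the rate under the SAP rule (12% or 29%). Let m be the share of an arm that is rescued or missing not at random. Let k be the imputed response rate as a multiple of the rate in the other subjects, p/(1 − m). The rate from the printed flow is then

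p + m × k × p/(1 − m).

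Assumed ranges are m = 10–30% for dupilumab and 10–15% for upadacitinib, with the same k in both arms.

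| k | Smallest difference (m = 30%, 10%) | Largest difference (m = 10%, 15%) |
|---|---|---|
| 0 | 17.0 | 17.0 |
| 0.25 | 29.8 − 13.3 = 16.5 | 30.3 − 12.3 = 17.9 |
| 0.5 | 30.6 − 14.6 = 16.0 | 31.6 − 12.7 = 18.9 |
| 1 | 32.2 − 17.1 = 15.1 | 34.1 − 13.3 = 20.8 |

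Differences are taken before rounding. For k above 0 both arm rates rise, and the difference can move either way. The lowest power in the grid (17.1% against 32.2%, unadjusted) is 99.95%.

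**The case against.** The strongest reply is that this is labelled sample code. It serves two branches, omits its merging steps, does not code the composite and never creates the flag or NRI variables. A programmer must complete it from the text, and the text states the rule correctly more than once. `ALL` is the right input for the MI branch, so what is missing is a branch switch. All of this stands: the slip does not show that the production program is wrong. It remains true that the only code printed for the primary method contradicts that method.

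Other points that stand in part:
- The before-and-after responder exception cannot apply at Week 16, the last Period 1 visit. It can apply at the earlier visits used for ranked endpoints.
- The printed code defines EASI 90 as a score of at most 0.9 times baseline, which is only a 10% reduction. The illustration uses the 90% reduction of Appendix H 2.2 and assumes the same flow for the composite, so it is not the literal output of the code. That threshold is a separate error.
- The route through the COVID-19 flag depends on a derivation that is not shown.
- With six strata, the average cell is 440/6, about 73 subjects, and 0.88^73 is about 0.01%. Zero cells matter only for small strata, and the documents give no stratum counts. The 12% rate is also the composite rate, while the code counts EASI 90. SAS was not run, so nothing is claimed about how PROC STDRATE treats a missing `CASE`.

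**Conclusion.** The concern holds, and it should be fixed. The mismatch between `ALL` and `ALLF`, the absence of a printed rescue step and the missing `CASE` value can all be read directly from the code without assumptions.

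Only the size depends on assumptions. The documents do not determine the size or direction of a shift, and k = 1 is an upper case. Topical rescue is offered only after a poor response, and the imputation conditions on earlier visits, so a low k is more likely. At k = 0.25 the shift is under one point either way. What is at stake is fidelity of the primary estimate to its stated rule and a sensitivity analysis that adds no check. Power and the estimand are not at stake.

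**What to change.** In SAP Appendix H 3.0:

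1. For NRI-MI, start the analysis from the overridden data, for example `DATA ALL; SET ALLF;` before the treatment selection. Keep `ALL` as the input for the MI path.
2. In both paths, print a step that sets response to 0 at every visit after first rescue, whatever the COVID-19/MAR flag says.
3. Use `CASE=SUM(RESP1,0)` or a count table with the SPARSE option, so that a cell without responders counts as 0.

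The cost is a few lines of code. The method text, data collection and sample size do not change.
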